## 6.0 Study Design and Procedures

All human subjects research will be conducted at the Institute for Health Research and Policy at UIC. Some portions of the data analyses conducted by Co-I [name] may take place at the University of Chicago. [name] role involves guiding the data analyses and writing up results for presentation and publication. [name] will only have access to a deidentified dataset and will not have any responsibility for recruitment, enrollment, consent, or data collection, and will never be able to access any participant contact information.

**Design Overview.** Participants will complete baseline assessments and a one-week EMA wave while they continue their usual pattern of cigarette use. After their first EMA week, participants will be randomized (within sex) in a 1:1 ratio to receive either SREC pods in their usual flavor (n=60) or pods in their choice of flavor (n=60). Participants assigned to the flavor choice condition can select from the four available SREC flavors (tobacco, menthol, watermelon, and blueberry) based on their preference and satisfaction with the flavor throughout the trial. All participants will receive brief behavioral counseling about reducing their cigarette use and switching to the SREC. After an initial week of using SREC and reducing the number of cigarettes smoked, participants will complete another EMA week assessing patterns and responses to use of both products. Participants will receive 12 weeks of SREC pods; complete daily reports of product use along with bi-weekly check-ins through the end of the 12-week trial, and then complete a one-month follow-up. Female participants of childbearing age (55 years old and younger) will provide urine for a required pregnancy test every 5 to 6 weeks and will be removed from the study if the test indicates a pregnancy. The total study duration for participants is 18 weeks. Table 1 shows the timeline of assessments, procedures, and modality.

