**Table 1: Timeline of Assessments and Procedures**

Week	Procedures	Modality	Visit Duration (in minutes)
0	Screening eligibility	On-line and phone	
1	CO; pregnancy test; baseline questionnaires on tablet (if not already completed); vital signs; height and weight; EMA training; go home with EMA and smoke usual cigarettes	In-person visit	90-120
2	De-brief EMA; CO; Counseling about reduction and switch; brief questionnaire; given week supply of SREC; daily reports of use	In-person visit; daily text/web reports of use	60
3	Return used pods; CO; Brief counseling to problem solve reduction and switch; given new week supply of SREC; start EMA	In-person visit; daily text/web reports	40
4	Debrief EMA week; return used pods; CO; brief review of progress and problem-solve; given 2-week supply of SREC	In-person visit; daily text/web reports of use	40
5	Daily reports of use via text/web	Daily Text/web reports of use	
6	Brief check-in to give next 2-week supply of SREC; return used pods; CO; continue daily reports of use via text/web; pregnancy test	In-person visit; daily text/web reports of use	20
7	Daily reports of use via text/web	Daily Text/web reports of use	
8	Brief check-in to return used pods; given next 2-week SREC supply; CO; continue daily reports of use via text/web	In-person visit; daily text/web reports of use	20
9	Daily reports of use via text/web	Daily Text/web reports of use	
10	Daily reports of use via text/web	Daily text/web reports of use	
11	Brief check-in to return used pods; CO; given next supply of SREC; continue daily reports of use via text/web; pregnancy test	In-person visit; daily Text/web reports of use	20
12	Daily reports of use via text/web	Daily text/web reports of use	
13	Daily reports of use via text/web	Daily Text/web reports of use	
14	End-of-treatment full assessment battery; CO; vitals; height and weight; collect SREC device and remaining pods; daily reports of use surveys end	In-person	60
18	Brief follow-up about cigarette and ENDS use over past month	Web/phone based	15

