E. **Carbon-monoxide (CO) level** in expired air will be measured using a digital monitor at each study visit allowing us to examine changes in CO over time along with changes in patterns of cigarette and SREC use. There are no required qualifications or credentials for the use of a carbon monoxide (CO) monitor. It is a very basic device that simply requires a subject to exhale into a disposable (single use), mouthpiece attached to the digital monitor. All staff involved in the implementation will be trained in the protocol, which includes the following:

1. A member of the research staff will insert a new mouthpiece, turn the monitor on and hand the monitor to the participant.
2. The participant will be instructed to inhale, hold the breath for 15 seconds, and then exhale the entire breath through the mouthpiece into the digital monitor while following the on-screen prompts.

F. **Urine pregnancy tests** will be administered to female participants of childbearing age (defined as 55 years old and younger) during the Week1/Enrollment visit and every 5 to 6 weeks during the study; those with positive test results (a result indicating pregnancy) will be removed from the study.

G. Other **vital signs** will be measured at study visits including height and weight (baseline and end of treatment), blood pressure and pulse (at every study visit).

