## 6.4. Specimen Collection

Urine test results will be collected from female participants to determine whether or not they are pregnant before study enrollment (Week1) and every 5 to 6 weeks thereafter until study completion. There will be no storage of collected urine. The urine samples and test sticks will be disposed of immediately after a successful pregnancy test has been conducted and recorded by study staff.

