## **11.0 Data and Safety Monitoring**

This trial will be monitored by [name]. (PI), [name]. (Co-I), [name] (Data Manager), and an independent Data Safety Monitoring Board (DSMB) that will be chaired by a medical safety monitor: [name], MPH, FAAP, Professor of Pediatrics, College of Medicine, UIC. The DSMB will meet at the start of the trial to review the study protocol, safety and ethical issues, and to approve plans for data integrity. [name], [name], and [name] will meet weekly during the data collection phase to review and monitor the following items: participant accrual, participant complaints, participant drop-out, reasons for drop-out, adverse events, and any other problems related to study participation. Data accuracy and completeness will also be monitored weekly. During active recruitment, the DSMB will join these data review meetings quarterly to monitor participant safety.

The data report will be updated on a weekly basis and will include: participant accrual, participant complaints, participant drop-out, reasons for drop-out, adverse events, and any other problems related to study participation. The report will also include preliminary data on cigarette and SREC usage on a participant basis.

An AE is defined as any untoward medical or psychological event experienced by a patient during or as a result of his/her participation in the study that represents a new symptom or an exacerbation of an existing condition whether or not considered study-related based on appropriate medical judgment. SAEs are any adverse experience that results in any of the following outcomes: death, life-threatening event/illness, inpatient hospitalization or prolongation of existing hospitalization, persistent or significant disability/incapacity, pregnancy resulting in a congenital anomaly/birth defect, or any event requiring medical or surgical intervention to prevent permanent impairment or damage. In this study, this is defined as physician confirmed diagnosis of any of the following: angina pectoris, heart attack, stroke, transient ischemic attack, heart failure, coronary angioplasty or bypass surgery, peripheral vascular disease, and cancer (except for non-melanoma skin cancer). Non-SAEs are all adverse events that do not meet the above criteria for "serious."

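### A positive pregnancy test takes a randomised woman out of the study without saying whether outcome data continue, and the birth-defect criterion for a serious event has no planned route of ascertainment

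*Combined protocol and SAP*

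**What the plan says.** **Removal.** Section 6.0, Design Overview, states that a woman aged 55 or younger "will be removed from the study if the test indicates a pregnancy". Section 6.3, item F, has it that "those with positive test results (a result indicating pregnancy) will be removed from the study", and the Weeks 5-13 paragraph of section 6.0 says the same. No further data collection after removal is described. For participants who leave early, section 11.0 mentions only an effort to recover the device and pods.

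**Testing period.** Section 6.4 describes tests "before study enrollment (Week1) and every 5 to 6 weeks thereafter until study completion". Tables 1 and 2 list tests at weeks 1, 6 and 11 only. The week-11 row of Table 1 reads "Brief check-in to return used pods; CO; given next supply of SREC; continue daily reports of use via text/web; pregnancy test". The week-14 row reads "End-of-treatment full assessment battery; CO; vitals; height and weight; collect SREC device and remaining pods; daily reports of use surveys end", with no pregnancy test.

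**Serious events.** The general list in section 11.0 includes "pregnancy resulting in a congenital anomaly/birth defect". The next sentence begins "In this study, this is defined as physician confirmed diagnosis of any of the following" and continues with cardiovascular diagnoses and procedures and cancer; a congenital anomaly is not among them. Section 13.3 includes congenital anomaly in its own definition of a serious event, with IRB notice within 24 hours.

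**Follow-up.** Section 11.0 schedules adverse event queries at visits up to week 14. Sections 6.2 and 11.0 also accept events that staff learn of between visits. Participation lasts 18 weeks, and the week-18 contact is a web or phone survey on product use.

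**The concern.** Two things are left open, both concerning women whose pregnancy is found after randomisation at week 2.

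First, leaving the study can mean no more product, no more assessments, or both. Elsewhere the plan keeps these apart. Section 6.1 lets dispensing stop during a quit attempt, and section 6.2 lets the investigator, medical monitor or DSMB stop dispensing; neither says that the participant leaves. Only pregnancy is tied to leaving the study. If that includes data collection, the protocol itself creates a post-randomisation exit before the primary endpoint. Pregnancy plausibly changes smoking, so these are cases where missing at random is hard to defend.

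Second, the plan treats nicotine in pregnancy as a risk (sections 7.0 and 11.0), tests for pregnancy, and names a birth defect as a serious outcome, yet gives no step by which the study would learn of one. Whether the criterion applies at all is unclear from section 11.0.

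**Working it through.** **1. When the exit falls.** Randomisation and first product are at week 2, and the primary endpoint is at week 14, 12 weeks later. The tests after randomisation are at weeks 6 and 11.
- Exit at week 6: 6 − 2 = 4 of 12 treatment weeks observed, 8 missing.
- Exit at week 11: 11 − 2 = 9 of 12 observed, 3 missing.

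Either way the week-14 visit and week-18 survey are lost if removal covers assessments. The observed weeks still enter the mixed model that yields the week-14 estimate (section 9.0). The abstinence outcome needs smoking status and CO at the end of treatment, and section 9.0 gives no rule for missing status.

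**2. How many women.** The documents give neither the number of women at risk nor a pregnancy rate. Assumed: 20 to 60 women, 1% to 15% pregnancies per year, and 10 weeks between the week-1 and week-11 tests. Expected removals = women × annual rate × 10/52.
- Low: 20 × 0.01 × 10/52 = 0.04
- High: 60 × 0.15 × 10/52 = 1.73

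So about 0 to 2 in the whole trial.

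**3. Effect on power.** The plan's own figure comes first. Section 12.0 allows 10% attrition, 120 × 0.90 = 108, or 54 per arm, and states power 0.80 for abstinence of 31.5% against 10%. With a two-sided 0.05 test (0.05 is stated only for aim 4 and assumed here), pooled variance under the null and no continuity correction:
- null SE = √(2 × 0.2075 × 0.7925 / 54) = 0.0780
- alternative SE = √((0.315 × 0.685 + 0.10 × 0.90) / 54) = 0.0752
- power = Φ((0.215 − 1.96 × 0.0780) / 0.0752) = 0.795, which reproduces 0.80.

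With removals added on top of the 10% attrition:

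| Further loss | Abstinence power |
|---|---|
| none | 0.795 |
| 1 in one arm | 0.792 |
| 2 in one arm | 0.789 |
| 1 per arm | 0.788 |
| 2 per arm | 0.780 |

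The worst row costs 0.795 − 0.780 = 0.015. It is 4 women, more than step 2 expects.

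For the primary rate ratio of 0.75 no dispersion is stated. A pure Poisson calculation gives power of at least 0.995, so the stated 0.80 implies a negative binomial dispersion of about 0.18 to 0.21. Using that implied value, 2 lost per arm moves 0.800 to 0.785, again 1.5 points.

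**4. Whether a birth could be seen.** Assume conception no earlier than about week −1, given the negative week-1 test, and term birth 38 weeks after conception: −1 + 38 = week 37. That is beyond the week-14 end of scheduled queries and the week-18 end of participation, whether or not the woman is removed.

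**5. Testing period.** Weeks 1, 6 and 11 are 5 weeks apart, which fits section 6.4. On the same spacing the next test would fall at 11 + 5 = 16 to 11 + 6 = 17. Product is collected at week 14 and week 18 is remote, so no visit is scheduled then. The wording and the tables agree only if study completion is read as something earlier than week 18.

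**The case against.** The main objection is size, and it stands. Birth control is required, women trying to conceive are excluded, and the 10% attrition allowance covers 12 people. Data before removal inform the primary estimate, and section 12.0 already plans pattern-mixture and selection-model sensitivity analyses. It is also fair that removal is undefined, so loss of the week-14 data is a reading of the text and not a stated intention, and that consent pages, not available here, may say more.

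Three stronger readings are tempting, and the documents do not support them.

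- *Removal makes a birth defect unobservable.* The 18-week horizon does that for a birth; a woman who stayed in would not be followed to delivery either. Nor is it impossible for a report to arrive, because events learned of outside visits are recorded. What is missing is a planned route.
- *The last test at week 11 costs week-14 outcomes.* A pregnancy that no test detects leads to no removal, so that woman stays and contributes data. That 3 of the 12 product weeks (25%) follow the last test is a separate fact and not a source of missing outcomes.
- *Section 6.4 flatly contradicts the tables.* The spacing agrees. Only the end point is unclear.

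None of this tells a site whether to keep collecting data after a positive test, or whether and how a birth defect is to be learned of and reported.

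**Conclusion.** The point holds as a low-cost clarification, not as a threat to the trial's conclusions. As written, the removal rule takes a randomised woman out of outcome collection at week 6 or 11 because of a post-randomisation event. The birth-defect criterion is listed in two places, left out of the study-specific definition in a third, and has no planned ascertainment in any.

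The expected number is about 0 to 2 women, resting on the assumed 20 to 60 women at risk and 1% to 15% pregnancies per year. Even 2 lost per arm beyond planned attrition costs about 1.5 points of power, and losses within the 12 already allowed for cost nothing. Any bias is limited by the retained earlier data and the planned sensitivity analyses; the abstinence outcome is the more exposed. The case for change rests on safety ascertainment and clear instructions, not on power.

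**What to change.** 1. In section 6.0 (Design Overview and Weeks 5-13) and section 6.3, item F, state what removal covers. Word it so that, whatever the sponsor and medical monitor decide about the product, a participant who consents stays in the existing smoking-outcome collection (daily surveys, week 14, week 18) and adverse event collection.
2. Reconcile the general list and the study-specific list in section 11.0 with section 13.3, so that it is clear whether a congenital anomaly is a serious adverse event in this study. If it is, record each pregnancy and obtain its outcome by phone. Section 13.2 destroys the name-to-ID code at the end of funding, so it would need an exception for these cases.
3. Reconcile the end of testing in section 6.4 with Tables 1 and 2. The schedule itself is for the sponsor and medical monitor to set.

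The cost is protocol and consent wording, a few outcome calls after week 18, and longer retention of the identity link for rare cases. No new visit is needed.

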**Table 1: Timeline of Assessments and Procedures**

Week	Procedures	Modality	Visit Duration (in minutes)
0	Screening eligibility	On-line and phone	
1	CO; pregnancy test; baseline questionnaires on tablet (if not already completed); vital signs; height and weight; EMA training; go home with EMA and smoke usual cigarettes	In-person visit	90-120
2	De-brief EMA; CO; Counseling about reduction and switch; brief questionnaire; given week supply of SREC; daily reports of use	In-person visit; daily text/web reports of use	60
3	Return used pods; CO; Brief counseling to problem solve reduction and switch; given new week supply of SREC; start EMA	In-person visit; daily text/web reports	40
4	Debrief EMA week; return used pods; CO; brief review of progress and problem-solve; given 2-week supply of SREC	In-person visit; daily text/web reports of use	40
5	Daily reports of use via text/web	Daily Text/web reports of use	
6	Brief check-in to give next 2-week supply of SREC; return used pods; CO; continue daily reports of use via text/web; pregnancy test	In-person visit; daily text/web reports of use	20
7	Daily reports of use via text/web	Daily Text/web reports of use	
8	Brief check-in to return used pods; given next 2-week SREC supply; CO; continue daily reports of use via text/web	In-person visit; daily text/web reports of use	20
9	Daily reports of use via text/web	Daily Text/web reports of use	
10	Daily reports of use via text/web	Daily text/web reports of use	
11	Brief check-in to return used pods; CO; given next supply of SREC; continue daily reports of use via text/web; pregnancy test	In-person visit; daily Text/web reports of use	20
12	Daily reports of use via text/web	Daily text/web reports of use	
13	Daily reports of use via text/web	Daily Text/web reports of use	
14	End-of-treatment full assessment battery; CO; vitals; height and weight; collect SREC device and remaining pods; daily reports of use surveys end	In-person	60
18	Brief follow-up about cigarette and ENDS use over past month	Web/phone based	15

**Baseline/Enrollment Visit Week 1.** The first visit begins with the final set of screening assessments: CO > 3ppm and negative pregnancy test for female participants. Once the screening is complete, participants who remain eligible will start the consent process. Staff describe the study, answer all questions, ensure understanding of the study information, and re-assess interest in participating. Participants who remain interested will be asked to sign the informed consent form. Participants will complete the baseline questionnaire on a tablet, and participants will have vital signs taken (blood pressure, heart rate, height, weight). Participants will also be trained on the EMA protocol (see below for more details) and given instructions to go home and smoke as they usually do. **The purpose of this first EMA week is to provide baseline data about the participant's smoking pattern which will be compared to their SREC/cigarette use pattern after switching.**

**Week 2 Visit.** Participants will complete a brief questionnaire and complete an expired CO assessment. Study staff conduct a debriefing interview to review the EMA week and their compliance with the protocol. Participants will be randomly assigned to the two flavor conditions, stratifying for gender. Those participants assigned to the choice condition will select from four SREC flavors (tobacco, menthol, watermelon, and blueberry) based on their preference. Participants assigned to the usual flavor condition will receive tobacco pods if they smoke regular cigarettes and menthol pods if they smoke menthol cigarettes. Participants in both conditions will receive **brief behavioral counseling** (see below for more details) on reducing their combustible cigarette use and using SREC as a substitution for cigarettes. Starting this week, participants begin to receive daily email or text prompts (based on participant's preferred mode of communication) to complete a brief online survey on their use of cigarettes, SREC, and non-SREC e-cigarette use each day.

**Week 3 Visit.** Participants will bring back all used and unused pods for adherence counts, complete a brief questionnaire about subjective reactions and potential adverse effects from SREC, and complete the CO assessment. Study staff review their progress with reducing their smoking and switching to SREC and continue brief behavioral counseling about reducing smoking and substituting SREC. Participants will be told that their goal is to completely switch. Participants will receive feedback on their compliance with the first EMA week and additional training to ensure accurate reporting of both SREC and cigarettes on the app. Participants go home with another week supply of SREC, begin the second 7-day EMA wave, and continue completing daily reports.

**Week 4 Visit.** Similar to the week 3 visit, except that participants will again debrief their EMA week for compliance and problems; complete assessments; and review their progress with switching to SREC. Participants will receive a 2-week supply of SREC and continue completing daily reports.

**Weeks 5-13.** Participants will return to the study office every 2 to 3 weeks to return pods, receive a new supply, and complete CO assessments. During the week, they will continue completing daily reports. Additionally, female participants of childbearing age will provide a urine sample every 5 to 6 weeks; those with positive test results (a result indicating pregnancy) will be removed from the study.

**Week 14 (End-of-Treatment).** Participants return to the study office to complete a full assessment battery and return the SREC device and all pods. They will be encouraged to continue to stay off/reduce all combustible cigarettes but will not receive any more study provided SREC pods.

**Week 18 (One Month Follow-up).** Participants will receive an email or text prompt to complete a brief web-based survey (phone if needed) about their cigarette and ENDS use during the past month as well as motivation and confidence to continue to stay off combustible/use ENDS in the future.

All study procedures are being done for research purposes; none are part of their health services or care.

## **6.1. Behavioral Intervention**

Participants in both conditions will receive brief behavioral counseling on several cigarette reduction strategies, including substitution of cigarettes with the SREC. Participants will be told to carry the SREC with them as they would their cigarettes, and to use the SREC when they feel the urge to smoke. Participants will

be told that it may take a few days to adjust to the SREC and a pattern of use, but that each day they should try to reduce the number of cigarettes smoked. Once participants have a week of experience with the SREC, they will be encouraged not to carry their usual cigarettes with them as another strategy of reducing their cigarette use. Staff will work with participants to set individual goals for reduction during this first week, with the goal of achieving at least 75% reduction in the number of combustible cigarettes smoked by the end of the week, and all encouraged to reduce further. Participants will be told that they should strive for complete switching after the first week. Participants will also be told not to use any other tobacco or nicotine products during their participation in the study.

The behavioral intervention is based on [name] prior work on a recently completed clinical trial evaluating treatment components to help smokers who were unmotivated to quit, to reduce and to attempt to quit. This treatment included a behavioral reduction component, which focused on strategies to help smokers systematically cut down on cigarettes. We are adapting this brief behavioral intervention by also providing coaching on how to use the SREC as a replacement for some cigarettes throughout the day.

Fidelity and staff competence at providing the intervention will be measured, assured, and maintained throughout the study in multiple ways. First, standardized training on delivering the intervention will be provided by [name]. Training will involve 40 hours (some self-study and review; others in-person, both individual and group learning activities). Training will include both didactic presentations and role-playing scenarios. Second, we will implement a tiered program of evaluating competence in delivering the intervention. Individual role-play sessions will be evaluated by [name] for adherence and skillfulness. Once staff role-play meets performance criteria, staff will be certified for observed participant visits. Participant visits will be observed and evaluated by [name] until staff independence is certified. Third, all staff will attend weekly group supervision with [name] to discuss cases, concerns, and challenges. Fourth, at the end of each study visit containing treatment delivery, study coaches will complete a self-assessment checklist of critical intervention behaviors and materials delivered and document the duration of the study visit. These records, stored in REDCap, will be subject to periodic review. Finally, 10% of all staff's treatment visits will be observed by [name] throughout the study and evaluated for protocol adherence using a standardized rating scale. Coaching staff with scores falling below 85% of the adherence standard will receive additional supervision, observation, and feedback. If adherence falls below 75%, the coach must complete "booster" training and be recertified in role-playing before resuming interactions with intervention participants.

Some participants may decide that they want to quit smoking altogether during their study involvement. We will support their quit efforts by adapting the behavioral intervention strategies from cutting down to quitting. This will include coping with urges and cravings, preparing for high-risk situations (i.e., situations that are likely to trigger urges to smoke), and encouraging social support. Health coaches will ask participants their preference on continuing to use the SREC during their quit attempt. We will honor participant preference and stop or continue dispensing additional SREC pods during their quit attempt.

